### **Recruitment:**

The study will recruit up to 3060 participants including 60 hospitalized patients from multiple locations. These will include SHC COVID testing sites, Stanford Health Care

300 and 500P locations (the Emergency Department and other in-patient wards particularly M7, the COVID ward), as well as the front entrance of Stanford hospital and several locations on Campus. We will also be recruiting folks from the bay area community for our study. Participants will fall into two categories: i) those receiving a CLIA certified nasal swab COVID-19 test at SHC at the moment of recruitment, and ii) those not.

We will be recruiting a high-risk population because we will be recruiting from a pool that includes people who are seeking medical attention and/or participating in COVID-related research studies. Feasibility and validity of the tests will be evaluated in the high-risk population. We will be additionally recruiting a low-risk population to assess feasibility in the general population. Hospitalized patients will provide information on concordance between the CLIA COVID test and the home saliva test in patients over a five day period when we expect to see a mix of positive and negative tests.

To increase the number of SARS-CoV-2 positive saliva samples, we will accept deidentified and deactivated saliva samples from external sources, including Guatemala. All of these external sources will have DUA/MTA in place and will have institutional approval and have received written informed consent from all participants for the local trials, including the sharing of these samples with Stanford University for the current trial.

**Inclusion and Exclusion criteria:**

(as noted above)

**Consent**

Potential participants will be approached by dedicated clinical research coordinators and study volunteers. They will be asked if they have an interest in participating and if so, whether they have an internet data-enabled cell phone capable of uploading high resolution photographs. Interested participants will then be directed to the digital e-consent implemented in REDCap on the mobile web browser. The CRC will be available to answer questions. The participants will also be provided an email and contact phone information for questions.

For the pediatric population, informed consent will be given by the legal guardian after they have been given the opportunity to answer any and all of the questions they may have and assent will be provided for children able to understand and complete the assent form (generally at least 7 years old).

Consent and Assent form will include a request to share access to their medical records for review of the results of any CLIA certified COVID test and any medical condition that might affect the veracity of testing. It will also include a request to observe the participants in-person or via video conferencing.

After consent, participants will receive a bag with materials for multiple home based tests as well as instructions on their phone via REDCap on how to use the test.

## Test Protocol

The REDCap survey will include a video demonstration of the test procedure. In addition, written instructions for use (IFU) will be available.

Participants will be asked to carry out as many tests as are included in the bag (most likely between one and two) on a daily basis until they are used up.

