**Analysis of the Feasibility Outcomes**

Analyses of all feasibility outcomes will be performed in the outpatient analysis set.

The concordance of the test results will be compared to the results of PCR testing. We will calculate the proportion in agreement (# of tests where SnapDx and PCR testing agree/# total tests), the proportion correctly identified as positive (# of tests SnapDx-positive/# PCR-positive), and the proportion correctly identified as negative (# of tests SnapDx-negative/# PCR-negative). A threshold of 80% overall agreement and 85% agreement in the positive tests will indicate the home test is feasible.

Percent confidence in interpretation of the results and that instructions were followed correctly will be summarized as 1) percent of respondents stating that they are at least 80% confident in their interpretation and 2) median and interquartile range of reported confidence levels. Results will be reported separately for participants and technicians.

The proportion of participants who call technical support will be presented and the frequency of the reason for the call will be presented. The proportion of tests that have a sufficient amount of saliva to reach the indicator line will be presented.

The feasibility outcomes will be presented separately by demographic characteristics in a subgroup. For example, we will evaluate whether the concordance is comparable across different age groups, between men and women, etc.

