## Data Acquired

Data acquired on all participants in this study will include

- 1) A baseline demographics survey collecting age, sex, and race/ethnicity, education levels, socio-economic background and COVID-19 vaccination status
- 2) A symptom survey filled in by the participant (one per test)

Additional data acquired on the positive/at-risk and the low-risk participants includes:

- 3) A survey to collect confidence in interpretation and in following the instructions (one per test)
- 4) An associated image of the at-home LAMP assay test result (one per test)
- 5) A follow-up survey for the usability comments (once)

Data collected on participants who have a CLIA COVID-19 test performed within 24 hours of the home saliva test will additionally include:

1. A medical chart review for the results of any CLIA COVID-19

2. Technicians will additionally provide an evaluation of their confidence in interpreting the participant-provided images using a survey identical to the one shown to participants
3. Also included will be the additional documentation for the participant to follow the local healthcare authorities and CDC guidelines for COVID-19 related process.

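### The per-test feasibility indicators have no first-test rule and no consistent unit, so first and repeat use can be mixed and first-use difficulty may be understated

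*Combined protocol and SAP*

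**What the plan says.** Repeat use by the same person is planned, but the number of kits is not fixed. The Consent section says "participants will receive a bag with materials for multiple home based tests". Test Protocol asks people to "carry out as many tests as are included in the bag (most likely between one and two) on a daily basis" until none are left.

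Data Acquired sets the collection unit item by item:

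- "A survey to collect confidence in interpretation and in following the instructions (one per test")
- "An associated image of the at-home LAMP assay test result (one per test")
- "A follow-up survey for the usability comments (once")

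Analysis of the Feasibility Outcomes then uses three different denominators:

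- **Tests.** Sample sufficiency is reported this way: "The proportion of tests that have a sufficient amount of saliva to reach the indicator line will be presented". Overall PCR agreement is the number "of tests where SnapDx and PCR testing agree/# total tests".
- **Respondents.** Confidence in interpretation and in having followed the instructions is given as a percentage of respondents. The survey is completed per test, and no rule says which test is used.
- **Participants.** Technical-support calls are a proportion of participants.

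General Considerations specifies Agresti-Coull 95% intervals. No section restricts an analysis to the first test, splits results by test order, or deals with two tests from one person. The only breakdown planned is by demographic characteristics.

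**The concern.** A second test is not a replicate of the first. The procedure has several steps: collecting saliva, two timed stages in hot water, reading a colour and taking a photograph. By the second kit the user has done all of this once and has seen a result. Some users may also not get as far as the second kit, and Handling of Missing Data already expects surveys to be missing for some tests.

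An average over one or two kits therefore depends on how many kits were in the bag and who used them. If second attempts go better, or if people who struggled are less likely to finish, the pooled figure will make the test look easier than it is for a new user. A larger sample does not remove that. Separately, two results from one person are likely to be correlated, and a simple binomial interval ignores this.

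**Working it through.** The documents give no sample-size, power or precision figure for the feasibility indicators, so there is no stated figure to reproduce. The share of people doing a second test and the first- and second-use rates are not given either. All rates below are assumptions.

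**1. Which indicators are exposed**

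| Indicator | Collected | Denominator in the analysis | Exposed? |
|---|---|---|---|
| Participant-technician discrepancy (primary) | image per test | no analysis given | unit undefined |
| Confidence in reading (secondary 1) | per test | respondents | unit undefined |
| Instructions followed (secondary 2) | per test | respondents | unit undefined |
| Sample sufficiency (secondary 4) | not listed separately | tests | yes |
| PCR agreement | per test | tests | yes |
| Technical-support calls (secondary 3) | not listed separately | participants | no |
| Usability comments | once | not stated | no |
| On-site usability cohort, 120 people | one test each | not stated | no |

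**2. Effect of learning.** Let p1 be the first-use success rate, p2 the second-use rate and r the share who do a second test.

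Pooled rate = (p1 + r × p2) / (1 + r)

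Overstatement of first-use success = r / (1 + r) × (p2 − p1)

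| Share repeating, r | r/(1 + r) | Gain 0 | Gain 5 | Gain 10 | Gain 15 points |
|---|---|---|---|---|---|
| 0.25 | 0.20 | 0 | 1.0 | 2.0 | 3.0 |
| 0.50 | 0.33 | 0 | 1.7 | 3.3 | 5.0 |
| 1.00 | 0.50 | 0 | 2.5 | 5.0 | 7.5 |

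Example with r = 1, p1 = 75% and p2 = 85%: (75 + 85)/2 = 80.0%, which is 5 points above first use. With little learning the effect is small. If problems fall from 10% to 8% and 90% repeat, the pooled problem rate is (10 + 0.9 × 8)/1.9 = 9.1%, a shift of 0.9 points.

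**3. Effect of differential completion alone.** Suppose there is no learning: each person's second outcome equals the first, and p1 = 75%. First-use successes go on to a second test with probability 0.9 and failures with probability 0.6.

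- Share repeating: 0.75 × 0.9 + 0.25 × 0.6 = 0.825
- Second-test successes per person: 0.75 × 0.9 = 0.675
- Pooled rate: (0.75 + 0.675)/(1 + 0.825) = 78.1%, or 3.1 points too high

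If both groups repeat with the same probability, the shift is zero.

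**4. Effect on the interval.** Take 1500 people (the planned size of each outpatient group), two tests each, and 80% success. With within-person correlation ρ, the effective sample size is 3000/(1 + ρ).

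| ρ | Effective n | Agresti-Coull 95% interval |
|---|---|---|
| 0 (as the plan implies) | 3000 | 78.5% to 81.4% |
| 0.5 | 2000 | 78.2% to 81.7% |
| 1 (same as first tests only) | 1500 | 77.9% to 81.9% |

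In an illustrative demographic subgroup of 120 people with two tests each, the interval is 74.5% to 84.6% if the 240 tests are treated as independent. It is 71.9% to 86.2% on 120 first tests.

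**The case against.** The strongest reply is that the product is meant for repeated surveillance. The Rationale describes people testing every morning, so an average over uses could be a legitimate target. That does not rescue the pooled figure. An average over whichever one or two kits were in the bag estimates neither first-use nor practised-use performance. Reporting the two separately serves both purposes.

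Other points stand and limit the concern:

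- **Scope.** A reader might infer that every feasibility indicator is pooled over kits. The documents do not support that. Pooling is explicit only for sample sufficiency and PCR agreement. Confidence and instruction-following have an undefined unit, and the analysis section gives no calculation for participant-technician discrepancy.
- **Single-use evidence.** The 120 people in the Usability/Feasibility section take one test each, so no second kit dilutes their ratings. They are tested at the study site, however, and that survey does not cover every secondary outcome.
- **Self-selection.** A reader might infer that only capable users reach the second kit. The documents put the kits in one bag and ask people to use them all, so selection can arise only through non-completion. The plan proposes multiple imputation under missing at random and sensitivity analyses, but does not say whether an unused kit counts as missing. Imputation would not separate first use from practised use in any case.
- **Decisions.** The 80% and 85% thresholds apply to PCR agreement. The other indicators have no pass mark, and the documents give no rates from which to judge whether a threshold would be crossed.

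**Conclusion.** The point holds as a gap in definition with a possible bias. For the per-test indicators, the plan fixes neither the unit nor the test order, one person can count twice, and the intervals assume independence. On assumed gains of 5 to 15 points, first-use difficulty would be understated by 2.5 to 7.5 points if everyone repeats and by 1.0 to 3.0 points if a quarter do.

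It would be going too far to say that first-use difficulty is understated. The direction is plausible, but the documents report neither a learning effect nor a repeat share. The bias is zero if bags hold one kit, or if there is neither learning nor differential completion.

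**What to change.** In Analysis of the Feasibility Outcomes:

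1. Make each participant's first self-run test the unit for participant-technician discrepancy and for secondary outcomes 1, 2 and 4. The discrepancy analysis itself has to be written in, since the section contains none.
2. Tabulate second tests separately by test order, with the number of people given two kits and the number who completed both.
3. For any figure still pooled over tests, including PCR agreement if it stays per test, use an interval that allows for clustering by participant, such as GEE or a cluster bootstrap.

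In the per-test survey listed under Data Acquired, record the test number. The documents do not say that order can be recovered from upload times, and a failed first test that was never uploaded would make the second look like the first.

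The cost is SAP wording, one survey field, one extra table and slightly wider intervals. In the example of 1500 people at 80%, the interval goes from 78.5%–81.4% to 77.9%–81.9%. Part of the narrower width came from counting correlated results as independent.

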### *Test description*

[figure not shown]
Test materials: saliva collection tube, small handheld centrifuge, test kit (plasticware) The test kit should be stored in a regular fridge (4C) at the location of the participant - prior to use.

The test materials include a cartridge containing a tube with closed reagents into which the participant will provide the saliva sample. Participants will be asked to provide 1ml of saliva into the collection tube, after which they will close the cap of the cartridge. They will be asked to pour boiling water into a mug and place the tube into the boiling water for 3 minutes. At the end of 3 minutes, they will then place the tube back in the mug of water for 40 minutes. At the end of 40 minutes, they remove the tube and note the color (pink/ orange = negative, yellow = positive). They will take a photograph of the tube against a given white photocard (provided in the kit) and upload it to the website. After filling in the short (<1 minute) symptom questionnaire and the short usability (<20 seconds) questionnaire they will dispose of the tube in the trash.

At that point, **if the test result is negative** (no evidence of infection) then they will be asked to do nothing other than fill in a survey and upload the image of the tube via study app. **If the test result is positive** they will be instructed to behave as if they might be infectious in their home and outside of their home (maximizing the use of masks and distancing) and asked to take a CLIA nasal swab test at their nearest SHC testing site at their earliest opportunity.

Our study provides the option for the participants to take a PCR nasal swab test at Stanford Health Care when their SnapDx tests result or the saliva direct PCR test done by the lab shows a positive SARS-CoV-2 result. Our study will cover the cost of the PCR nasal swab test for the participants.

Figure: Color change in tubes. Yellow color is a positive result

Left sample spiked with random plasmid DNA, right sample spiked with COVID-19 control RNA, at 50 genomes/ $\mu$ L.

## Data Acquired

Data acquired on all participants in this study will include

- 1) A baseline demographics survey collecting age, sex, and race/ethnicity, education levels, socio-economic background and COVID-19 vaccination status
- 2) A symptom survey filled in by the participant (one per test)

Additional data acquired on the positive/at-risk and the low-risk participants includes:

- 3) A survey to collect confidence in interpretation and in following the instructions (one per test)
- 4) An associated image of the at-home LAMP assay test result (one per test)
- 5) A follow-up survey for the usability comments (once)

Data collected on participants who have a CLIA COVID-19 test performed within 24 hours of the home saliva test will additionally include:

1. A medical chart review for the results of any CLIA COVID-19

2. Technicians will additionally provide an evaluation of their confidence in interpreting the participant-provided images using a survey identical to the one shown to participants
3. Also included will be the additional documentation for the participant to follow the local healthcare authorities and CDC guidelines for COVID-19 related process.

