## Study Population:

The study population consists of a diverse group of Stanford faculty, staff, and students, and the local Santa Clara County community and specific external sources with known positive saliva samples and DUA/MTA in place. More specifically, there are three sub-populations to address our aims:

- 1) (Positive population) Hospitalized patients (N=15)
- 2) (High risk and positive population) People from Bay area community and external sites with known positive saliva samples and DUA/MTA in place; Those with a suspected COVID infection seeking testing within the Stanford Health Care system (N=1500)
- 3) (Low risk population) People from Bay area community; Students on the Stanford campus and employees at Stanford Health Care (N=1500)

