### **Primary Feasibility Outcome:**

An indicator for discrepancy in interpretation of findings by participant versus by technician via photo (interrater reliability)

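### Technician assessment of photos is tied to a CLIA test within 24 hours and the technician's reading is nowhere listed, so the low-risk group is likely to yield sparse, selected data on the primary feasibility outcome

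*Combined protocol and SAP*

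**What the plan says.** The Primary Feasibility Outcome is "An indicator for discrepancy in interpretation of findings by participant versus by technician via photo (interrater reliability". Secondary outcome 1 is an indicator of low confidence in the reading, for participant and technician alike. The Analysis of the Feasibility Outcomes section places all feasibility outcomes in the outpatient set, with no CLIA condition. The Recruitment section gives the low-risk group (1500 in Study Population) its purpose: "We will be additionally recruiting a low-risk population to assess feasibility in the general population".

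The Data Acquired section collects one image and one participant confidence survey per test from the at-risk and low-risk groups. The technician item stands in a separate list, introduced by "Data collected on participants who have a CLIA COVID-19 test performed within 24 hours of the home saliva test will additionally include". It reads: "Technicians will additionally provide an evaluation of their confidence in interpreting the participant-provided images using a survey identical to the one shown to participants". No other technician item is listed.

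Under Test description, a participant who reads the test as positive is "asked to take a CLIA nasal swab test at their nearest SHC testing site at their earliest opportunity". One who reads it as negative only completes a survey and uploads the image. The same section offers a study-paid swab if either the SnapDx test or the laboratory saliva PCR is positive.

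**The concern.** A comparison of two readings of the same photo needs the photo and two readers. It needs no PCR result, so a CLIA condition serves no purpose for this outcome. Followed as written, the condition withholds technician confidence from most of the group recruited to represent ordinary users. If the technician's reading is collected through the same survey, it withholds that too.

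The condition is also linked to the result. In the low-risk group, the planned routes to a swab start from a positive SnapDx or a positive laboratory saliva PCR. Self-read negatives, where a positive tube misread at home would sit, are the tests least likely to be checked. At stake is whether the study can say how often ordinary users and technicians disagree.

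**Working it through.** The plan gives no expected number of technician-read photos and no precision target for this outcome, so there is no figure to reproduce. The question is how many low-risk photos would be read under the rule as written.

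**Inputs.** From the documents: N = 1500 low-risk participants; technician item only with a CLIA test within 24 hours; Agresti-Coull 95% intervals (General Considerations). Assumed, because the documents give no values: prevalence 1% (range 0.2-5%), SnapDx sensitivity 85%, specificity 99% (range 95-99%), share u of self-read positives swabbed within 24 hours 50% (range 25-100%). One test per participant is counted.

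**Step 1: swabs only after a self-read positive.** Self-read positives = N × [prev × sens + (1 − prev) × (1 − spec)] = 1500 × (0.01 × 0.85 + 0.99 × 0.01) = 1500 × 0.0184 = 27.6. Read by a technician = 27.6 × 0.5 = 13.8, or 0.9% of 1500. Over the stated ranges the result runs from 4.4 to 135 participants (0.3% to 9.0%).

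**Step 2: the laboratory saliva PCR route.** In the base case, infected participants with a negative SnapDx number 1500 × 0.01 × 0.15 = 2.25. Ignoring false positives of the saliva PCR, this route adds about two people at most.

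**Step 3: CLIA tests for other reasons.** Let a share b of the group have one within 24 hours, whatever their result. Self-read positives read = 27.6 × [b + (1 − b) × 0.5]. Self-read negatives read = 1500 × 0.9816 × b.

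| b | Positives read | Negatives read | Read, % of 1500 | Positives among those read |
|---|---|---|---|---|
| 0 | 13.8 | 0 | 0.9% | 100% |
| 1% | 13.9 | 14.7 | 1.9% | 49% |
| 2% | 14.1 | 29.4 | 2.9% | 32% |
| 5% | 14.5 | 73.6 | 5.9% | 16% |
| 10% | 15.2 | 147.2 | 10.8% | 9% |

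Self-read positives are 1.84% of the group, so at b = 5% they are over-represented about nine-fold (16.4 / 1.84 = 8.9).

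**Step 4: effect on a crude rate (illustration).** Suppose disagreement is 1% for self-read negatives and 15% for self-read positives; both figures are assumed. At b = 5% the read subset shows 0.164 × 15% + 0.836 × 1% = 3.3%. The whole group has 0.0184 × 15% + 0.9816 × 1% = 1.3%.

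**Step 5: precision.** Agresti-Coull half-widths at about 95% agreement are 17 points with 14 photos (13 agreeing), 3.9 points with 150, 2.6 points with 300 and 1.1 points with 1500.

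**The case against.** The strongest reply is that the restricted item is the technician's confidence, not the reading. Photos exist for every test, and the outcome and its analysis set carry no CLIA condition. The data list is also plainly incomplete: it omits the participant's own result, support calls, sample sufficiency and the saliva PCR result, so silence about the technician's reading may be loose drafting. This stands in part. That the reading is restricted too is an inference from the survey being identical to the participant's. On the other view, however, the plan provides for a technician reading nowhere, and technician confidence for secondary outcome 1 remains restricted on the plain wording.

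A reader might infer that the low-risk photos read would be mainly self-read positives. The documents do not support this. Recruitment divides participants by CLIA test at enrolment without mapping this to risk group, the low-risk group includes health care employees, and the Rationale mentions a random selection of negative home tests for specificity, without size or procedure. In the base case self-read positives fall below half once about 1% of the group has a CLIA test for another reason. Over-representation is what can be said.

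A reader might also infer that the result must be biased. That does not follow either. Handling of Missing Data specifies multiple imputation under missing at random, with sensitivity analyses, and the participant's own reading is an observed variable. But that section expects a small amount of missing data. Here imputation would supply about 99% of low-risk technician data in the base case, 94% at b = 5% and 89% at b = 10%. With few self-read negatives read, the model would lean heavily on the high-risk group. The problem is then weak information and dependence on the model.

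**Conclusion.** The concern holds in a limited form. On the text alone, the one technician item is conditional on a CLIA test that the feasibility outcomes do not need, and no technician reading is listed for any group. Because most low-risk self-read negatives have no planned swab, technician data from that group are likely to be sparse and to over-represent self-read positives. The size depends on assumed prevalence, accuracy and swab timing, and on a share of other CLIA testing that the documents do not give: about 1% of the 1500 in the base case, about 6% with 5% other testing. The stated purpose of the low-risk group is poorly served for secondary outcome 1 and, by fair inference, for the primary feasibility outcome. This is more than a missing detail, because a stated collection rule conflicts with the stated outcomes and analysis set.

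**What to change.** In Data Acquired, move the technician item to the list for all at-risk and low-risk participants, so that it depends only on an uploaded photo. List two data items, the technician's reading and the technician's confidence, both recorded blind to the participant's reading.

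If reading every photo is too much work, read all self-read positives plus a pre-drawn random sample of self-read negatives in each risk group, and weight by the inverse of the sampling fraction. A 20% sample, for example, would in the base case mean 0.20 × 1472.4 + 27.6 = about 322 low-risk photos.

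In Analysis of the Feasibility Outcomes, add the participant-versus-technician discrepancy rate by risk group, with its Agresti-Coull interval or a weighted equivalent if photos are sampled. At present that section specifies agreement between SnapDx and PCR, and its 80% and 85% thresholds refer to that comparison. Moving the data item alone would not create the missing analysis.

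The cost is some extra reading time for existing technicians on images already uploaded. No new participants or procedures are needed.
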